

Outcome(s):
	
Primary outcome
 
 - The primary outcome at 6 month will be the continuous smoking abstinence from target quit date to the 6-month follow-up visit, ascertained by self-report (self-report of no smoking from target quit date) and confirmed by urinary levels of anabasine (<3 ng/ml). - The primary outcome at 12- and 24- months will be the self-reported 7-day point prevalence abstinence (not having smoked cigarettes within the preceding week), confirmed by urinary levels of anabasine (<3 ng/ml). 
Secondary outcomes
 
 - Secondary smoking cessation outcome will alternate definitions of the smoking cessation outcome: as the primary outcome, but allowing up to 5 cigarettes in total and a 2-week 'grace period' after the target quit date, self-reported 7-day point prevalence abstinence, all confirmed by urinary level of anabasine. We will also apply alternate definitions of the validation of exposure to tobacco smoking with: exhaled CO levels (CO<10 ppm) and NNAL (<10 pg/ml creat) and exposure to nicotine (from tobacco cigarettes, ENDS or NRTs) with urinary levels of cotinine. We will further report on change in the self-reported number of cigarettes smoked per day (CPD), with 50% reduction in CPD from baseline to follow-up considered as successful reduction. - Concentrations of urinary tobacco-specific nitrosamines (TSNAs), volatile organic compounds (VOCs), aldehydes and polycyclic aromatic hydrocarbons (PAHs) for all participants. Participants will complete a detailed questionnaire to account for other sources of exposure to these chemicals. - Respiratory symptoms (self-report) - Oxidative stress assessed by 8-OHdG and 8-isoprostane concentrations in both exhaled breath condensate (EBC) and urine; - Cardiovascular risk factors (CVRF) assessed by HDL- and LDL-cholesterol, HbA1c, creatinine, blood pressure levels, waist circumference, and body mass index. - Adverse events (AEs), serious adverse events (SAEs) following international standards. - Mood, anxiety and sleep quality (Self report) - Pulmonary function, measured by conventional pulmonary function tests and by multiple breath washout (MBW). - Structural and functional outcomes as ventilation and perfusion of the lung, measured by MRI. - Micronuclei (MN) in buccal epithelium - Olfactory function assessed by the Burghart Sniffin' Sticks (odor identification score (OIS)). - Dry-hit recognition - Detection of inflammatory biomarkers

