9.2.2 Assessment of secondary outcomes

The secondary outcomes will be measured as described for the primary endpoint.

Secondary smoking cessation outcome will be measured with a self-reported 7-day point prevalence abstinence (not having smoked cigarettes within the preceding week), again confirmed by urinary level of anabasine, and change in the self-reported number of cigarettes smoked per day (CPD) with 50% reduction in CPD from baseline to follow-up considered as successful reduction, measured as above.

For alternate validation methods of the primary and secondary outcomes, we will use CO-levels, which will be measured with a Micro Smokerlyser®; Bedfont Scientific Ltd.

Respiratory symptoms will be assessed by questionnaires:

- COPD Assessment Test (CAT), Modified Medical Research Council (MMRC) Scale, Asthma Test (ACT/ ECRHS)

Each Urine sample will be split into six aliquots to quantify cotinine and anabasine (see above), PAH metabolites, VOCs, propylene glycol, TSNAs, 8-OHdG and 8-isoprostanes, since no analytical method can measure all the compounds together. The different compounds will be estimated as follows:

- Concentrations of urinary cotinine and anabasine, VOCs, TSNAs and PAHs will be measured
- Oxidative stress will be assessed by quantifying 8-OHdG and 8-isoprostane concentrations in both EBC and urine
- We will adapt the method for analyzing urinary TSNAs from Xia et al.³⁰ After enzymatic hydrolysis with a β -glucuronidase solution, the urine sample will be extracted using solid phase extraction (SPE) columns, and analyzed by LC/MS/MS.
- We will use a high performance liquid chromatography (HPLC) method developed by the IST laboratory to analyze PAHs (1- and 2-Naphthol and urinary 1-OHP).

Exhaled breath condensates (EBC) other than CO will be performed in all participants at the Lausanne site during the first as well as the outcome visit (baseline and 6 months), based on guidelines from the American Thoracic Society (ATS)/European Respiratory Society (ERS) Task Force for EBC collection⁸⁷. EBC will be sampled with an EcoScreen II system (total exhaled volume of about 120 L). After collection, each sample will be aliquoted. To avoid auto-oxidation of fatty acids (potential impact on 8-isoprostane levels), we will add tert-butyl hydroxytoluene and rapidly freeze the sample. The samples will be stored at -70°C for a maximum of 1 month.⁹⁰

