- Number of cigarettes smoked per day (CPD), self-reported, at baseline, TQD, phone visits and 6 months visit
- Change in number of cigarettes smoked per day (CPD), self-reported. Successful reduction defined as 50% reduction in CPD.
- Respiratory symptoms assessed by questionnaires:
 - Change in COPD Assessment Test (CAT) from baseline to month 6, score from 0-40 (regarded as continuous)
- Change in cardiovascular risk factors from baseline to month 6, assessed by
 - Total cholesterol (continuous)
 - HDL-cholesterol (continuous),
 - LDL-cholesterol (calculated, continuous),
 - triglycerides (continuous),
 - blood pressure levels (continuous),
 - heart rate (continuous),
 - waist circumference (continuous) and
 - body mass index (continuous).
- AEs (in categories from adjudication committee)
- SAEs (in categories from adjudication committee)

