6.2 Derivation of Outcomes

Comments to secondary smoking cessation outcomes:

- Smoking is allowed during the grace period.
- The number of cigarettes smoked since the last visit is recorded as a categorical variable (1-5 cigarettes, >5 cigarettes). If the participant smoked more than once a day cigarettes in the last 7 days, the value is recorded as numeric variable. For secondary smoking cessation outcomes, we will assume the median value for the categorical variable. I.e. if a subject records 2 times to smoke 1-5 cigarettes, we assume him to be over the limit of 5 cigarettes.

Table 3: Derivation of primary and secondary outcomes.

Outcome	eCRF sheet	Variable	Variable type	Derivation	Outcome type
Primary: continuous smoking abstinence from target quit date to the 6-month follow-up visit AND	cig_ecig	quit_smoke_again	Binary: No, Yes	{ [Week 1/2/4/8, and month 6] quit_smoke_again == No AND quit_tobacco_inhale ==	Binary
		quit_tobacco_inhale	Binary: No, Yes		
	cig_ecig_6m	quit_smoke_again	Binary: No, Yes		
		quit_tobacco_inhale	Binary: No, Yes		

CTU Bern	SAP for: ESTxENDS	Version: 1-02.0
-----------------	-------------------	---------------------------------

CTU Bern	Template: Statistical Analysis Plan (SAP)	Version: 03
	Code: CS_STA_TEM-11	Valid from: 28-02-2019 to 05-06-2023

urinary level of anabasine (<3 ng/ml) OR	to be defined	to be defined	to be defined	No} AND {x < 3 if x!=missing, vs_co2_level<10 if x==missing & vs_co2_level ==missing}
CO level	vital_6m	vs_co2_level	Continuous	
Secondary outcomes				
continuous smoking abstinence from target quit date to the 6-month follow-up visit AND	Cig_ecig, cig_ecig_6m	quit_smoke_again, quit_tobacco_inhale	Binary: No, Yes, Binary:No, Yes	{[Week 1/2/4/8, and month 6] quit_smoke_again == No AND quit_tobacco_inhale == No} AND
urinary level of NNAL (<10 pg/ml creat) OR	To be defined	To be defined	To be defined	{y < 10 if y!=missing, x<3 if y==missing & x!=missing, vs_co2_level<10 if y==missing & x==miss- ing & vs_co2_level!=missing }
urinary level of anabasine (<3 ng/ml) OR	To be defined	To be defined	To be defined	
CO level	Vital, Vital_6m	vs_co2_level	continuous	
Continuous smoke abstinence allowing a 2-week grace period after TQD	cig_ecig / cig_ecig_6m	quit_smoke_again quit_tobacco_inhale	Binary: No, Yes	[Week 4, Week 8, and 6 months] sum(quit_smoke_again == No) >= 2 AND sum(quit_tobacco_in- hale == No) >= 2

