urinary level of NNAL (<10 pg/ml creat) OR	To be defined	To be defined	To be defined	{ y < 10 if y!=missing, x<3 if y==missing & x!=missing, vs_co2_level<10 if y==missing & x==missing & vs_co2_level!=missing }	
urinary level of anabasine (<3 ng/ml) OR	To be defined	To be defined	To be defined		
CO level	Vital, Vital_6m	vs_co2_level	continuous		
Self-reported 7-day point prevalence abstinence at 6 months	cig_ecig_6m	quit_smoke_again, quit_smoke_7days	Binary: No, Yes	quit_smoke_again == No AND quit_smoke_7days == No	Binary
Self-reported 7-day point prevalence abstinence at 6 months AND	cig_ecig_6m	quit_smoke_again, quit_smoke_7days	Binary: No, Yes Binary: No, Yes	{ quit_smoke_again == No AND quit_smoke_7days == No} AND { x < 3 if x!=missing, vs_co2_level<10 if x==missing & vs_co2_level ==missing}	Binary
urinary level of anabasine (<3 ng/ml) OR	To be defined	To be defined	To be defined		
CO level	Vital, Vital_6m	vs_co2_level	continuous		
Self-reported 7-day point prevalence abstinence AND	cig_ecig_6m	quit_smoke_again, quit_smoke_7days	Binary: No, Yes	{quit_smoke_again == No AND quit_smoke_7days == No} AND	Binary
urinary level of NNAL (<10 pg/ml creat) OR	To be defined	To be defined	To be defined	{y < 10 if y!=missing, x<3 if y==missing & x!=missing, vs_co2_level<10 if	
urinary level of anabasine (<3 ng/ml) OR	To be defined	To be defined	To be defined		

CTU Bern	SAP for: ESTxENDS	Version: 4.02.0
----------	-------------------	---------------------------------

CTU Bern	Template: Statistical Analysis Plan (SAP)	Version: 03
	Code: CS_STA_TEM-11	Valid from: 28.02.2019 5.6.2023

CO level	Vital, Vital_6m	vs_co2_level	continuous	y==missing & x==missing & vs_co2_level!=missing}	
Number of cigarettes smoked per day (CPD)	cig_ecig / cig_ecig_6m	quit_more1perday	continuous (number of cigarettes per day in the last 7 days)	[BL, TQD, phone visits and 6-month visit] quit_more1perday	Continuous
Change in the self-reported number of cigarettes smoked per day in the last 7 days	cig_ecig / cig_ecig_6m	quit_more1perday	continuous (number of cigarettes per day in the last 7 days)	(quit_more1perday[month 6] / quit_more1perday[day 0]) >= 0.5 IF [month 6]{contact_estab_yn == Yes AND quit_smoke_again == Yes AND quit_smoke_7days == Yes AND quit_smoke_nperday == ">=1x/Tag"} ELSE TRUE	Binary
CAT	cat / cat_6m	q1 to q8	radio (0 to 5)	sum(q1 to q8)[cat_6m] – sum(q1 to q8)[cat]	continuous (score scale 0-40, difference can be 0-40 as well)

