6.5 Missing data

Missing values in the primary outcome will be categorized as persistent smokers. We intend to obtain full follow-up data on all randomized participants.

Missing data in secondary smoking cessation outcomes will be treated as the primary outcome. If more than 5% of data is missing, all other secondary outcomes will be imputed, assuming values to be missing at random. Each outcome will be imputed separately to ensure robust imputation models. We will use all baseline variables (see Table 2) and outcome measures at all time points as predictors in the imputation models. The two intervention groups will be imputed separately. Variables with more than 50% missing values will not be used for the imputation model. Binary variables with a frequency of less than 5% in one category will be omitted from the predictors, levels of categorical variables with a frequency of less than 5% in one category will be combined with another level in a sensible way. Continuous variables will be log-transformed if it improves normality (checked by Shapiro-Wilks test and QQ plots). If predictors are too highly correlated among each other, we will only consider the predictor which is more strongly correlated with the outcome. In case of missing baseline covariates, ~~W~~we will use multiple imputation by chained equation. We will impute values using predictive mean matching for continuous and ordinal variables, logistic regression for binary variables, and a multinomial regression model for categorical variables with more than two levels. In total, fifty imputed data sets will be generated, which will be analysed as described using Rubin's rules (Rubin 1987). We will compute stabilized inverse probability of censoring weights to take into account potentially informative censoring or outcome data.

CTU Bern	SAP for: ESTxENDS	Version: 4.02.0
----------	-------------------	------------------------

CTU Bern	Template: Statistical Analysis Plan (SAP)	Version: 03
	Code: CS_STA_TEM-11	Valid from: 28.02.2019 5.6.2023

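### SAP Table 3 scores the 50% smoking-reduction outcome the wrong way round, from day 0 instead of baseline, and sends participants not contacted at month 6 to success

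*Supplement*

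**What the plan says.** SAP 2.0, 6.1 states the outcome in words: "Successful reduction defined as 50% reduction in CPD". Protocol 9.0, 9.2.2 fixes the reference point: "50% reduction in CPD from baseline to follow-up considered as successful reduction". The protocol synopsis and section 11.4.3 also measure from baseline.

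SAP 2.0, 6.2, Table 3 turns this into code. The row for change in CPD tests "quit_more1perday[month 6] / quit_more1perday[day 0]) >= 0.5 IF [month 6]{contact_estab_yn == Yes". It then requires that the participant reports smoking again, has smoked in the last 7 days and smokes at least once a day. It closes with "AND quit_smoke_nperday == '>=1x/Tag'} ELSE TRUE". The ratio is therefore tested only in contacted daily smokers, and all others are TRUE.

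On missing values, SAP 2.0, 6.5 says: "Missing data in secondary smoking cessation outcomes will be treated as the primary outcome". For the primary outcome, missing means persistent smoker.

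**The concern.** The coded rule and the definition it should implement do not agree on direction, reference point or handling of absent participants. Reducing the number of cigarettes smoked is named in the primary objective (protocol 4.2), and this binary outcome is the SAP's derivation of successful reduction. If Table 3 is programmed as it stands, smokers who did not cut down are reported as successes and those who cut down most as failures.

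The Table 3 row is the same in SAP 1.0 and 2.0, so the inequality is unlikely to be an artefact of reading the PDF.

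**Working it through.** **What TRUE means.** Quitters do not meet the IF conditions and fall into the default branch, which is TRUE. TRUE must therefore mean success. Reading it as failure would make every quitter a failure.

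**Direction.** Reduction = 1 − (CPD at month 6 / CPD at reference). A reduction of at least 50% is a ratio of at most 0.5. Table 3 requires at least 0.5. Only a ratio of exactly 0.5 satisfies both.

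| Participant (baseline 20 per day) | Day 0 | Month 6 | Table 3 | SAP 6.1, protocol and SAP 6.5 |
|---|---|---|---|---|
| Cuts to 4, daily | 20 | 4 | ratio 0.2: failure | success |
| No change | 20 | 20 | ratio 1.0: success | failure |
| Increases | 20 | 30 | ratio 1.5: success | failure |
| Early cut, then 4 | 10 | 4 | ratio 0.4: failure | success |
| Early cut, then 8 | 5 | 8 | ratio 1.6: success | success (by accident) |
| Day-0 value 0, relapse to 20 | 0 | 20 | undefined | failure |
| Quit | – | – | success | success |
| Smokes less than daily | – | – | success | success |
| Not contacted | – | – | success | failure |

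**Denominator.** Randomisation is at the end of the baseline visit (protocol 7.3), 7 days before the target quit date (9.3.2). Intervention participants receive two devices and e-liquids at that visit (8.2.1). Table 3 describes CPD as covering the last 7 days, so for a call on schedule the day-0 value covers the week after randomisation and can be affected by allocation. Example: baseline 20, day 0 = 10, month 6 = 8. From baseline the reduction is 1 − 8/20 = 60%. From day 0 it is 1 − 8/10 = 20%, which would fail even with the inequality corrected. The row just above in Table 3 lists the baseline value of the same variable, so it is available.

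**Effect on the comparison.** Inputs from protocol Table 11.2-1 at 6 months, 586 per arm:
- quitters: 56 + 50 = 106 (ENDS), 11 + 56 = 67 (control)
- smokers: 111 + 340 = 451 (ENDS), 17 + 473 = 490 (control)
- lost: 29 in each arm

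Assumptions, because the documents give no figures: all continuing smokers smoke daily, day 0 equals baseline, and proportions rE (ENDS) and rC (control) of continuing smokers at least halve their CPD.

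- Intended: (quitters + r × smokers) / 586
- As written: (quitters + (1 − r) × smokers + lost) / 586

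With rE = 0.30 and rC = 0.20:
- Intended: (106 + 135.3)/586 = 41.2% versus (67 + 98)/586 = 28.2%, RR 1.46.
- As written: (106 + 315.7 + 29)/586 = 76.9% versus (67 + 392 + 29)/586 = 83.3%, RR 0.92.

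Other assumptions: 40% versus 30% gives RR 1.34 intended and 0.92 as written; 50% versus 30% gives 1.55 and 0.82.

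**When the direction changes.** The as-written difference in successes is (106 − 67) + (1 − rE) × 451 − (1 − rC) × 490 = 490 rC − 451 rE. It is negative whenever rE exceeds 490/451 = 1.09 times rC. With equal rates of 20% it does not reverse: as written (106 + 360.8 + 29)/586 = 84.6% versus 83.3%.

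**Losses alone.** With the inequality corrected but the default branch kept, 30% versus 20% gives (241.3 + 29)/586 = 46.1% versus (165 + 29)/586 = 33.1%, RR 1.39. Each arm gains 29/586 = 4.9 points.

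**The case against.** The strongest answer is that the intended definition is clear in SAP 6.1 and the protocol, so any programmer would correct an obvious slip. The intent is indeed not in doubt. But double programming (SAP 6.9) checks code against this same table, and SAP 2.0 makes the analyses unblinded. The correction should therefore be in the plan and not made silently in code. A slip in the inequality also does not explain the day-0 denominator.

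On absent participants, section 6.5 may be meant to override the default branch. That is possible, but the SAP does not say so, and the IF clause names the contact variable explicitly. The fair description is two passages in conflict. For contacted quitters and less-than-daily smokers the default of success is sensible: entry required at least 5 cigarettes a day.

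The outcome is secondary, and protocol 11.4.3 also plans mixed and joint models of CPD, so the reduction question does not rest on this line alone. That stands.

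Three stronger readings are tempting and not supported:
- A reader might infer that counting losses as successes favours ENDS. With equal losses it moves the RR from 1.46 to 1.39, towards the null. The history of changes records selective control-arm attrition without numbers; extra credited losses there would raise the control rate.
- A reader might take 451/586 (77%) and 490/586 (84%) as the share misclassified. Those are all expected smokers, not daily smokers, and the denominator makes some classifications right by accident.
- A reader might infer that quitters' CPD is missing and would be imputed from smokers. Section 6.2 says only "If the participant smoked more than once a day cigarettes in the last 7 days, the value is recorded as numeric variable"; how quitters are stored is not shown. SAP 2.0, 6.5 ties chained-equation imputation to missing baseline covariates, and the closing change note says censoring weights were used instead, although other sentences in 6.3.1 and 6.5 still speak of imputing outcomes.

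**Conclusion.** Wrong as written. The reversed inequality follows from the text alone. The day-0 denominator contradicts the protocol's baseline and is measured after randomisation. The default branch conflicts with SAP 6.5.

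The rule reverses the classification of most continuing daily smokers, whose number the documents do not give, and can change the direction of the estimated effect. The RRs shown rest on the protocol's expected cell counts, on the assumed reduction rates, on all smokers being daily smokers and on day 0 equalling baseline. The reversal comes from the inequality, not from the losses. The primary outcome and its analysis are not affected.

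**What to change.** Rewrite the Table 3 row as follows:
- contacted daily smokers at month 6: success if CPD at month 6 / CPD at baseline ≤ 0.5, otherwise failure;
- contacted participants who are not smoking or smoke less than daily: success;
- no month-6 contact, or missing: failure, as in SAP 6.5.

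State the boundary once, since the protocol synopsis uses at least 50% and section 11.4.3 uses more than 50%. Record the correction in the SAP's table of changes. The cost is SAP wording and recoding; the baseline value is already listed, so no new data are needed.

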OHdG and 8-isoprostane will be simultaneously determined in EBC, using a method adapted to Syslova et al.⁹⁰ After adding internal standards (isotopically labeled 8-OHdG and 8 isoprostane), 1 ml of EBC will be lyophilized and the residue dissolved in a water:methanol solution and immediately analyzed by a liquid chromatography–atmospheric pressure ionization tandem mass spectrometry (LC-ESI-MS/MS) method available at IST.

Cardiovascular risk factors (CVRF) will be assessed as follows:

- Blood collection: We will measure cardiovascular risk factors in blood by routine methods in clinical practice: Total-, LDL- and HDL-cholesterol, triglycerides, HbA1c (only for participants with diabetes) and creatinine.
- Blood pressure and heart rate will be measured by standard sphygmomanometer. After a 10-minute rest, the right arm blood pressure of a seated participant will be assessed three times at one-minute intervals. The two last blood pressures measures will be averaged to reduce variability.
- Height, weight (calculation of body mass index, BMI), and abdominal circumference

.We will query all participants if they had SARS-CoV-2 testing during the outbreak.

Pulmonary function will be assessed in a subgroup of 150 participants at the Bern site using conventional pulmonary function tests and by multiple breath washout. Pulmonary function test results will be interpreted according to the current ERS/ATS guidelines¹⁵¹ and in the case of evidence for COPD according to the current GOLD report¹⁵². MBW results will be analyzed according to the current ERS/ATS consensus statement⁷⁷.

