LDL cholesterol	calculated	calculated	Continuous (mmol/L)	lab_choles_total[vital_6m]-lab_choles_hdl[vital_6m]-(lab_triglyceride[vital_6m]/5)-lab_choles_total[vital]-lab_choles_hdl[vital]-(lab_triglyceride[vital]/5) [Friedewald formula]	continuous (mmol/L)
HDL cholesterol	vital vital_6m	lab_choles_hdl	continuous (mmol/L)	lab_choles_hdl[vital_6m] – lab_choles_hdl[vital]	continuous (mmol/L)
triglycerides	vital vital_6m	lab_triglyceride	continuous (mmol/L)	lab_triglyceride[vital_6m] - lab_triglyceride[vital]	continuous (mmol/L)
blood pressure	vital vital_6m	vs_bpressure_sys1-3, vs_bpressure_dias1-3	continuous (mmHg)	mean(vs_bpressure_sys1-3), mean(vs_bpressure_dias1-3)	continuous (mmHg)
heart rate (mean of the second and third measure)	vital vital_6m	vs_heart_rate_2 vs_heart_rate_3	continuous (bpm)	mean(vs_heart_rate_2, vs_heart_rate_3)[vital_6m] – mean(vs_heart_rate_2, vs_heart_rate_3)[vital]	continuous (bpm)
waist circumference	vital vital_6m	vs_waist_cm	continuous (cm)	vs_waist_cm[vital_6m] - vs_waist_cm[vital]	continuous (cm)
BMI	vital vital_6m	bmi	continuous (kg/m ²)	bmi[vital_6m] – bmi[vital]	continuous (kg/m ²)
Lab values					
Metabolites of nicotine:					

CTU Bern	SAP for: ESTxENDS	Version: 1.0
----------	-------------------	--------------

CTU Bern	Template: Statistical Analysis Plan (SAP)	Version: 03	
	Code: CS_STA_TEM-11	Valid from: 28.02.2019	Page 22 of 27

Anabasine	To be defined	To be defined	dichotomized at <3 ng/ml	anabasine < 3	Binary: <3ng/ml, ≥3ng/ml
Metabolites of TSNAs:					
NNAL	To be defined	To be defined	dichotomized at <10pg/ml	NNAL < 10	Binary: <10pg/ml, ≥10pg/ml

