Cholesterin (total)	vital vital_6m	lab_choles_total	continuous (mmol/L)	lab_choles_total[vital_6m] – lab_choles_total[vital]	continuous (mmol/L)
LDL cholesterol	calculated	calculated	Continuous (mmol/L)	lab_choles_total[vital_6m]-lab_choles_hdl[vital_6m]- (lab_triglyceride[vital_6m] /5)-lab_choles_total[vital]-lab_choles_hdl[vital]- (lab_triglyceride[vital] /5) [Friedewald formula]	continuous (mmol/L)
HDL cholesterol	vital vital_6m	lab_choles_hdl	continuous (mmol/L)	lab_choles_hdl[vital_6m] – lab_choles_hdl[vital]	continuous (mmol/L)
triglycerides	vital vital_6m	lab_triglyceride	continuous (mmol/L)	lab_triglyceride[vital_6m] - lab_triglyceride[vital]	continuous (mmol/L)
blood pressure	vital vital_6m	vs_bpressure_sys1-3, vs_bpressure_dias1-3	continuous (mmHg)	mean(vs_bpressure_sys1-3), mean(vs_bpressure_dias1-3)	continuous (mmHg)
heart rate (mean of the second and third measure)	vital vital_6m	vs_heart_rate_2 vs_heart_rate_3	continuous (bpm)	mean(vs_heart_rate_2, vs_heart_rate_3)[vital_6m] – mean(vs_heart_rate_2, vs_heart_rate_3)[vital]	continuous (bpm)
waist circumference	vital vital_6m	vs_waist_cm	continuous (cm)	vs_waist_cm[vital_6m] - vs_waist_cm[vital]	continuous (cm)
BMI	vital vital_6m	bmi	continuous (kg/m ²)	bmi[vital_6m] – bmi[vital]	continuous (kg/m ²)
Lab values					
Metabolites of nicotine:					

CTU Bern	SAP for: ESTxENDS	Version: 4.02.0
----------	-------------------	---------------------------------

CTU Bern	Template: Statistical Analysis Plan (SAP)	Version: 03	
	Code: CS_STA_TEM-11	Valid from: 28.02.2019 5.6.2023	Page 22 of 27

Anabasine	To be defined	To be defined	dichotomized at <3 ng/ml	anabasine < 3	Binary: <3ng/ml, ≥3ng/ml
Metabolites of TSNAs:					
NNAL	To be defined	To be defined	dichotomized at <10pg/ml	NNAL < 10	Binary: <10pg/ml, ≥10pg/ml

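### The LDL change formula in SAP Table 3 subtracts baseline HDL and triglycerides where they should be added back and uses a mg/dL divisor on mmol/L data, and the blood-pressure rule departs from the protocol (secondary outcomes only)

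*Supplement*

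**What the plan says.** SAP 2.0, section 6.1, places LDL cholesterol and blood pressure among the core secondary outcomes, under the line "Change in cardiovascular risk factors from baseline to month 6, assessed by".

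Table 3 in section 6.2 then gives LDL as "lab_choles_total[vital_6m]-lab_choles_hdl[vital_6m]- (lab_triglyceride[vital_6m] /5)-lab_choles_total[vital]-lab_choles_hdl[vital]- (lab_triglyceride[vital] /5) [Friedewald formula". The part at issue is how this expression ends: "lab_triglyceride[vital_6m] /5)-lab_choles_total[vital]-lab_choles_hdl[vital]- (lab_triglyceride[vital] /5) [Friedewald formula". SAP 1.0 has the same terms with the same signs: "lab_choles_total[vital_6m]-lab_choles_hdl[vital_6m]-(lab_triglyceride[vital_6m]/5)-lab_choles_total[vital]-lab_choles_hdl[vital]-(lab_triglyceride[vital]/5) [Friedewald formula". The lipid rows are all typed "continuous (mmol/L". The triglyceride row is a plain difference, "lab_triglyceride[vital_6m] - lab_triglyceride[vital".

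The blood-pressure row reads "mean(vs_bpressure_sys1-3), mean(vs_bpressure_dias1-3". It names both visit forms as sources, but the derivation itself carries no visit index and no subtraction. Protocol 9.0, section 9.2.2, takes three readings and states: "The two last blood pressures measures will be averaged to reduce variability". Protocol 2.0 already had this rule in substance, so the conflict did not arise from a later amendment. The heart-rate row of Table 3 uses readings 2 and 3, at 6 months minus baseline.

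SAP 6.3.1 analyses continuous secondary outcomes by linear models adjusted for the baseline value. SAP section 7 undertakes to list every departure from the protocol. Its Table 4 lists two, on the scope of follow-up and on blinding, and neither concerns blood pressure.

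**The concern.** A change in LDL is the 6-month LDL minus the whole of the baseline LDL. When baseline LDL is itself a difference (total cholesterol less HDL less a triglyceride term), subtracting it must turn its two minus signs into plus signs. The written expression leaves them negative. Whoever programs the row as it stands obtains a quantity that is not a change in LDL.

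The divisor raises a separate question. Cholesterol and triglycerides convert from mg/dL to mmol/L by different factors, so a divisor of 5 cannot hold in both units.

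For blood pressure, two governing documents give different averaging rules for the same outcome, and the SAP row does not say whether a 6-month value or a change is analysed.

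At stake are the interpretability and precision of secondary cardiovascular outcomes. There is also the record: an analyst who silently repairs the rows reports something that the plan does not specify.

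**Working it through.** The documents give no sample size or power for LDL or blood-pressure change between arms, so there is no stated figure to reproduce. The check evaluates the rules as written. TC, HDL and TG carry the suffix 6 (6 months) or 0 (baseline).

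**1. Sign.**
- As written: TC6 - HDL6 - TG6/5 - TC0 - HDL0 - TG0/5.
- Intended, same divisor: (TC6 - HDL6 - TG6/5) - (TC0 - HDL0 - TG0/5) = TC6 - HDL6 - TG6/5 - TC0 + HDL0 + TG0/5.
- Written minus intended: -2 × (HDL0 + TG0/5).

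This needs nothing beyond the SAP. For its size, assume baseline values in mmol/L and no true change (correct answer 0):
- HDL 1.0, TG 0.8: -2 × (1.0 + 0.16) = -2.32
- HDL 1.3, TG 1.5: -2 × (1.3 + 0.30) = -3.20
- HDL 1.6, TG 3.0: -2 × (1.6 + 0.60) = -4.40

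With a real change (TC 5.2 to 5.0, HDL 1.3 to 1.4, TG 1.5 to 1.3):
- As written: 5.0 - 1.4 - 0.26 - 5.2 - 1.3 - 0.30 = -3.46
- Bracketed, divisor 5: 3.34 - 3.60 = -0.26
- Bracketed, divisor 2.2: 3.01 - 3.22 = -0.21

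**2. Divisor.** Assumed conversion factors (not in the documents): 38.67 for cholesterol and 88.57 for triglycerides, mg/dL per mmol/L. The mmol/L divisor is 5 × 38.67/88.57 = 2.18, about 2.2. Using 5 overstates an LDL level by TG/2.2 - TG/5: 0.20, 0.38 and 0.76 mmol/L at TG 0.8, 1.5 and 3.0. In a change most of this cancels, as the -0.26 against -0.21 above shows.

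**3. Arm comparison.** A simulation of 300 trials of 1172 participants used these assumptions: LDL mean 3.2, SD 0.9, correlation between visits 0.75; HDL mean 1.4, SD 0.4, correlation 0.8; log TG mean 0.35, SD 0.5, correlation 0.6; true LDL effect -0.10. Mean estimate and standard error, adjusted for baseline LDL:
- Correct formula: -0.100, SE 0.035
- Bracketed, divisor 5: -0.099, SE 0.036
- As written: -0.097, SE 0.063

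The SE ratio is 0.063/0.035 = 1.8. As a check on the first line, the residual SD is 0.9 × √(1 - 0.75²) = 0.595, and 2 × 0.595/√1172 = 0.035. The precision is lost because adjusting for baseline LDL does not remove the stray HDL0 and TG0 terms. A second simulation (586 per arm, 400 trials, different assumed SDs and correlations) gave SE 0.045 correct and 0.063 as written, a ratio of 1.4.

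**4. Blood pressure.** For illustrative readings 140, 132 and 130, the SAP mean of three is 134.0 and the protocol mean of the last two is 131.0. For 128, 126 and 125 they are 126.3 and 125.5. The rules differ whenever the first reading differs from the mean of the other two.

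**The case against.** The best defence is that Table 3 is shorthand. The LDL row is labelled with the name of a known formula and sits under a heading about change, so the intent is clear. No code is shown, so one cannot say that the analysis was run this way. SAP 3.2 requires derived variables to be checked for outliers and unit consistency, SAP 6.9 requires double programming, and a mean fall of some 3 mmol/L in both arms would probably be noticed. The outcomes are secondary, and for cardiovascular risk factors the protocol itself expects only a 10 to 40% chance of detecting a difference between ENDS users and continuing smokers.

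The points on intent, code and stakes stand. The safeguards lower the risk but do not mend the specification: two programmers who follow the same wrong row will agree with each other.

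The defence also holds against four stronger readings that a reader might infer:
- **Everyone appears to fall by more than 3 mmol/L.** With no true change this needs HDL0 + TG0/5 above 1.5. It fails at HDL 1.0 and TG 0.8.
- **The treatment effect is biased.** Randomisation balances baseline HDL and triglycerides in expectation, and the simulated estimate barely moves (-0.097 against -0.100).
- **The wrong divisor distorts the comparison.** It distorts LDL levels. Once bracketed, the arm difference and its SE hardly change.
- **The missing blood-pressure subtraction changes the result.** Under baseline adjustment, the 6-month value and the change give the same arm difference. The row merely fails to say which is used.

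**Conclusion.** Both rows are wrong as written, for secondary outcomes only. The sign error and the blood-pressure conflict follow from the documents alone; the divisor rests on the assumed conversion factors.

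If the LDL row is followed literally, each participant's score is shifted by -2 × (HDL0 + TG0/5), about -2.3 to -4.4 mmol/L over the assumed baseline range. Mean changes per arm cannot then be interpreted, and the arm difference loses precision without material bias. The SE inflation of 1.4 to 1.8 depends on assumed SDs and correlations. In variance terms it runs from about 2.0 (1.4²) to 3.2 (1.8²), so no single multiple should be quoted.

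The blood-pressure averaging is an unlisted departure from the protocol. Its size depends on how far first readings differ from later ones, which the documents do not give.

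Nothing here shows that reported results are wrong, since the documents contain no code, and the primary outcome is not involved.

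**What to change.** Rewrite two rows of Table 3 and the matching code:
- LDL change = (TC6 - HDL6 - TG6/2.2) - (TC0 - HDL0 - TG0/2.2), all in mmol/L.
- Blood-pressure change = mean of readings 2 and 3 at 6 months minus mean of readings 2 and 3 at baseline, separately for systolic and diastolic. This matches protocol 9.2.2 and the heart-rate row.

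If the mean of three readings is preferred, list it in SAP Table 4 with a reason. State in the report which LDL and blood-pressure formulas were actually run. The cost is two table lines and a rerun of these outcomes; no new data are needed, because the readings and lipid values are already on the visit forms.
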